1.5 Preclinical and Clinical Experience

1.5.1 Preclinical Studies

The precise lineage of FoxP3-expressing regulatory (Treg) cells in humans is still being defined and debated [?]. In murine studies, numerous studies support the presence of both thymically-derived 'natural' Treg (nTreg) and

inducible Treg (iTreg). A major source of iTreg appears to be under the influence of retinoid acid and TGF- β in the gut-associated lymphoid tissue (GALT) [?]. iTreg versus nTreg have a phenotype consistent with recent TCR activation (CD45RA- CD62L- CD95+ CD31- CTLA4+). Miyara, et al. define two suppressive CD25++ FoxP3+ populations, which they term activated or resting and define using phenotypic markers that we plan to use in this project, including CD45RO/RA, CD62L, Ki-67, and CD31.

1.5.2 Clinical Studies

Mucosal immunotherapy (oral or sublingual) has been studied for the treatment of allergic rhinitis and more recently for food allergy [?????]. The majority of participants (85%) have been able to tolerate and successfully complete OIT treatment regimens with mild side effects that can be controlled by the occasional use of antihistamines.

There have been only two studies of carefully controlled peanut OIT with subjects characterized by double-blind oral food challenge (total of 62 subjects involved) [????]. Initial target maintenance doses were comparable (300-500 mg protein) and drop out due to adverse reactions was low (10-18%). Those subjects who reached maintenance achieved significant increases in the threshold dose of peanut required to provoke symptoms. Median threshold doses were >1000 mg protein after therapy (approximately 2 to 4 peanut kernels), well above the average estimated amount of exposure during an accidental ingestion. Only the study by Blumchen, et al. attempted to determine whether increased tolerance versus desensitization was achieved by holding all peanut exposure for two weeks prior to reassessing the threshold dose by repeat oral food challenge [?].

1.6 Risks

1.6.1 Risks of Investigational Product(s) / Intervention(s)

In previous studies of peanut oral immunotherapy, mild to moderate side effects of dose increases (done at study visits) have included: lung symptoms (e.g., cough, increased use of albuterol for individuals with asthma), GI tract symptoms (nausea, vomiting, diarrhea), skin symptoms (hives, itchiness) and nose symptoms (e.g. stuffiness) More rarely, similar side effects have also occurred during doses taken at home, especially when the child had an intercurrent illness (e.g., a cold), exposure to another allergen (e.g., during pollen season for those who have seasonal allergies), in association with exercise or when taken on an empty stomach [? ?]. Menses together with exercise has also been reported in one case as a potential co-factor for reactions to OIT [?]. Additional rare risks of OIT and food challenges are those of anaphylaxis and include respiratory obstruction (e.g., wheezing, coughing, and swelling of the voice box) and cardiovascular problems such as a drop in blood pressure or cardiovascular collapse. Most OIT studies to date have targeted a younger patient population. A 2011 study [?] of children aged 3 to 18 noted that peanut allergic patients over 10 years of age reacted at lower eliciting doses than those in the youngest tertile (< 5.5 years). They did not attempt to report on reaction severity. The median eliciting dose for the oldest age group was approximately 45 mg of peanut protein with an interquartile range of 4.5 to 200 mg peanut protein. In a study of the efficacy of anti-lgE for the treatment of adolescents and adults (13-59 years) with peanut allergy, the mean pre-treatment eliciting dose was 330 mg of peanut flour (range 1 - 2000 mg) [?].

1.6.2 Risk of Study Procedures

1.6.2.1 Double-blind placebo controlled food challenge (DBPCFC) Possible adverse events during DBPCFCs include: GI symptoms (vomiting, diarrhea or abdominal pain), respiratory symptoms (wheezing, coughing, laryngeal

15 of 68

edema, or hoarseness) or skin symptoms (hives, angioedema or pruritus). A severe adverse event, systemic anaphylaxis involving the above symptoms plus hypotension, circulatory collapse, upper airway (laryngeal) blockade and lower airway blockade (asthma) is also a potential risk. Risk of reaction is minimized by administering doses in a graded fashion, stopping at the first sign of objective symptoms, and treating reactions promptly.

- 1.6.2.2 Desensitization Procedure Possible reactions during the desensitization procedure may include adverse events: GI symptoms (vomiting, diarrhea or abdominal pain), respiratory symptoms (wheezing, coughing, laryngeal edema, or hoarseness) or skin symptoms (hives, angioedema or pruritus). Systemic anaphylaxis involving the above symptoms plus hypotension, circulatory collapse, upper airway (laryngeal) blockade and lower airway blockade (asthma) is also a potential risk. Reactions during desensitization following similar procedures in other studies involving hundreds of subjects to date have been mild. At home doses have very rarely been associated with serious adverse events (e.g., autoinjector epinephrine use) and no AEs have been reported to result in hospitalization or long term impairment to date. Subjects may also develop new or worsening atopic dermatitis (AD) or eosinophilic esophagitis (EoE) that is reversible with cessation of OIT.
- **1.6.2.3 Allergy Prick Skin Testing** Possible reactions during an allergy prick skin testing procedure may include itchy skin rash or hives, mild fever, fever symptoms, asthma, and lower blood pressure. There is also a very low risk of a severe adverse event, systemic anaphylaxis, involving the above symptoms plus hypotension, circulatory collapse, upper airway (laryngeal) blockade and lower airway blockade (asthma). All of these are treated with topical steroids, with inhaled albuterol, or, if necessary, with injections of epinephrine or other anti-allergic drugs.
- **1.6.2.4 Blood Draw** May aggravate a pre-existing anemic condition but this risk is negligible since the volume of blood to be drawn at each visit will be at most 3 ml/kg in pediatric participants and 1 unit of blood in adult participants. Blood draws will occur four times spread out over the 90 week study (See Section 7 for specific schedule). Other risks are those related to any needle puncture, including slight bruising, local infection, or the possibility of the participant fainting. The discomfort involved is minimal.

1.6.3 Risk of Concomitant Medications, Prophylactic Medications and Rescue Medications

The following are the risks associated with concomitant and rescue medications:

- Albuterol: dysrhythmia, hypokalemia, and hypersensitivity reactions.
- Epinephrine: dysrhythmia, hypokalemia, and hypersensitivity reactions.
- Diphenhydramine: urinary retention, blurred vision, delirium, and hypersensitivity reactions.
- Hydroxyzine: urinary retention, blurred vision, delirium, and hypersensitivity reactions.
- Ranitidine: urinary retention, blurred vision, dysrhythmia, hepatitis, pancreatitis, and hypersensitivity reactions.
- Corticosteroid: hyperglycemia/glycosuria, fluid retention, hypokalemia, hypernatremia, dysrhythmia, anxiety, delirium or other mental status changes, and hypersensitivity reactions.

1.7 Benefits

1.7.1 Benefits of Investigational Product(s) / Intervention(s)

The risks associated with participation in this study are minimal in relation to the potential benefits derived by both the subject and society. Subjects may derive two major benefits from the study. First, subjects may be desensitized to peanut and have a reduced risk of anaphylaxis from an accidental ingestion of peanut. Second, subjects may become tolerant and no longer need to avoid peanut. However, there may be no direct benefit to subjects by participating in the study.

Potential benefits to society include a better understanding of food hypersensitivity reactions, better methods to treat food allergic individuals, and an improved understanding of food allergens involved in the human immune response.

1.7.2 Benefits of Study Procedure(s)

NA

2 OBJECTIVES

2.1 Primary Objective(s)

To determine whether PN OIT induced clinical tolerance in the context of food allergy is significantly associated with the expansion of a specific regulatory T cell subset (CD45RA- CD25++ FoxP3++) that is thought to be inducible in the gut-associated lymphoid compartment and associated with immunological tolerance.

We will measure the change from baseline of induced Treg cells as a frequency of total CD4 T cells during active treatment and compare that between participants who achieve significant clinical tolerance (Tolerance and Partial Tolerance Groups as defined below) and those who do not (Treatment Failure Group).

2.2 Secondary Objective(s)

2.2.1 Clinical:

- To evaluate whether PN OIT induces increased tolerance, defined as a statistically significant increase in the median eliciting dose (ED) from DBPCFC1 to DBPCFC3.
- To evaluate whether PN OIT induces clinical desensitization, defined as 1) a median 10-fold or greater increase in ED from DBPCFC1 to DBPCFC2; 2) a statistically significant higher median ED at DBPCFC2 between active and control treatment; and 3) a significantly lower frequency of accidental ingestion reactions in active versus control treatment.
- To evaluate the safety of PN OIT.

2.2.2 Mechanistic:

- To determine whether PN OIT induces a statistically significant increase in the TCR clonal diversity of Treg
 populations during active treatment among participants who achieve increased clinical tolerance (Tolerance
 and Partial Tolerance Groups as defined in clinical endpoints) versus the Treatment Failure Group.
- To determine whether PN OIT suppresses mast cells by inducing a significant suppression of the median ED on end-point dilution skin testing in actively treated participants by the end of maintenance therapy.
- To determine whether PN OIT suppresses basophils as defined by a 10-fold suppression of peanut-specific basophil ED in actively treated participants by end of maintenance.
- To determine whether either mast cell or basophil suppression at the end of maintenance therapy is significantly associated with clinical outcomes following avoidance.

2.2.3 Exploratory:

- To describe the gene expression profiles and clonal diversity of regulatory and effector T cell subsets before
 and after OIT to better understand the phenotype and ontogeny of these subsets and potentially discover
 new therapeutic pathways.
- To engineer human MHC class II tetramers on common HLA backgrounds and map T cell epitopes of the dominant peanut allergens for use in validating earlier findings and for future studies of peanut-specific immune responses in humans.
- To determine whether microbial dysbiosis is associated with the development of desensitization, oral tolerance, or persistent gastrointestinal adverse events while on oral immunotherapy.

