1.2 Rationale for Selection of Study Population

This protocol is designed to identify participants who have persistent peanut allergy. By specifically targeting participants who are at the highest risk for life-long peanut sensitivity, we anticipate that we might maximize the benefits of desensitization and/or clinical tolerance induction. By including in our protocol design a post-therapy challenge after a significant allergen avoidance period, we will better distinguish true tolerance from desensitization and some of the immune changes associated with varying clinical outcomes. A blinded placebo control group is included, to control for possible changes in clinical sensitivity over time independent of therapy. The selection of older adolescents and adults will also allow us to better study immunological changes using assays that require blood volumes that would not be feasible to obtain in a younger population.

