3.1.2 Secondary Endpoint(s)

Secondary endpoints are:

Clinical:

- Tolerance:
 - The change in median eliciting dose (ED) from DBPCFC1 to DBPCFC3.
- Desensitization:
 - The change in median eliciting dose (ED) from DBPCFC1 to DBPCFC2.
 - The frequency of accidental ingestion reactions in active versus control treatment.
- Safety:
 - Anaphylaxis requiring more than 1 administration of epinephrine; or hospitalization.
 - Death as a result of the investigational product.
 - The rate of reported adverse advents due to accidental ingestions in the active versus placebo groups.

Mechanistic:

- The change in the TCR clonal diversity of in vitro allergen-expanded Treg cells and induced Treg cells measured by TCRβ CDR3 sequence clonotyping of sorted cells during active treatment among participants who achieve increased clinical tolerance (Tolerance and Partial Tolerance Groups as defined in clinical endpoints) versus the Treatment Failure Group.
- The change in ED of end-point dilution skin testing between actively treated and placebo treated participants following maintenance therapy.
- The change in ED of end-point dilution skin testing among actively treated participants following maintenance therapy and avoidance between clinical outcome groups.

- The change in peanut-specific basophil ED in actively treated participants at the end of maintenance and the end of avoidance between clinical outcome groups.
- The change in peanut allergen-specific IgG4 in actively treated participants by the end of maintenance between clinical outcome groups.
- The change in Ara h 2 specific surface and secreting B cells between baseline (measured after 12 weeks
 of treatment) and the end of maintenance.
- Statistically significant gene expression changes by transcriptional profiling of regulatory and effector T cell participants before and after OIT between clinical outcome groups.

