5.6 Modification or Discontinuation of Investigational Product(s) / Intervention Material(s)

5.6.1 Modification of Investigational Product(s) / Intervention(s)

Participants receiving active treatment who react to <1443 mg peanut protein during DBPCFC2 will be considered a treatment failure and be recommended to return to a strict peanut avoidance diet.

If the participant tolerates <4430 mg peanut protein during the DBPCFC3, he or she may elect to resume daily peanut protein dosing either at the highest tolerated dose during the challenge or 4000 mg peanut protein (whichever is less). If less than 4000 mg peanut protein, the daily dose will be increased by 25% every 2 weeks (\pm 4 days) as tolerated at the MGH CRC until they reach a dose of 4000 mg of peanut protein. They will continue on a dose of 4000 mg peanut protein for 1 year. At that time, they may elect to repeat a challenge.

At study end, those participants who are neither treatment failures nor achieve full tolerance, as determined by the DBPCFC3, may elect to have a nutrition consult to review a diet that would allow for the daily consumption of peanut protein at a dose that is tolerated without symptoms. The subject may also elect to resume strict avoidance. These subjects will continue to be followed at the MGH Food Allergy Center.

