7 STUDY VISITS AND PROCEDURES

Appendix 16.1 summarizes the schedule of events for the study.

7.1 Enrollment and Randomization

Participants will be recruited from oral immunotherapy-interested individuals who have contacted us in response to announcements and advertisements, referrals from Allergy/ Immunology Clinics, and by identification using the Partners Research Participant Data Registry. The referring physician may send potential participants and/or their

23 of 68

parents a recruitment letter. The letter will include contact information for study staff so the participant and/or their parents can opt-in to participate. This research study will be explained in lay terms to each potential research participant. The potential participant or participant's legal guardian will sign an informed consent form before undergoing any baseline study procedures. Participants age 14-17 will co-sign the consent form with their legal guardian. Participants age 7-13 will sign a child-specific assent form and their legal guardian will sign the consent form.

Participants enrolled as minors will be provided an adult consent form for signature when they reach age 18 and will be re-consented before any study procedures take place. Any "new adult" who refuses consent will be removed from the study. Participants who are deemed eligible for the study (see section 4) will be enrolled and assigned a unique participant number.

Following DBPCFC1, participants will be randomly assigned by the study statistician to treatment or placebo groups at a ratio of 3:1. Following DBPCFC2, assignment will be unblinded and placebo participants will be offered open-label active treatment following the same desensitization procedures (Modified Rush, Build Up and Maintenance).

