The placebo group will be used primarily to assess whether and to what extent there are more AEs associated with treatment. However, we will be able to also perform an intention to treat analysis of the primary outcome (difference in Treg proportion at the second blood draw from baseline) including the Placebo group. There is no expected effect on Treg in the placebo group and as above the comparison of interest is of outcomes within the actively treated participants who complete DBPCFC3. Estimating that 27% of active arm treatment achieve significant tolerance (n=8; see Figure 15.5) and that all Placebo group participants are defined as Treatment Failures after DBPCFC2 (n=10) and that the remaining Active Treatment participants will lose tolerance during avoidance (n=14), then we will have 100% power at an α level of 0.05 to detect the expected 1.5 X SD difference.

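### The tolerance objective credits OIT with a before/after rise in eliciting dose that has no comparator, no stated population and two different challenge dose ladders

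*Combined protocol and SAP*

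**What the plan says.** Section 2.2.1 states the objective: "To evaluate whether PN OIT induces increased tolerance, defined as a statistically significant increase in the median eliciting dose (ED) from DBPCFC1 to DBPCFC3". Section 3.1.2 gives the matching endpoint as "The change in median eliciting dose (ED) from DBPCFC1 to DBPCFC3". Neither names a comparison arm, a test or an analysis population.

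The desensitization objective, next in the same list in section 2.2.1, does have between-arm criteria. It asks for "a statistically significant higher median ED at DBPCFC2 between active and control treatment" and for fewer accidental-ingestion reactions than control.

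On the placebo arm, section 1.2 says: "A blinded placebo control group is included, to control for possible changes in clinical sensitivity over time independent of therapy". Section 9.1 says: "The placebo group will be used primarily to assess whether and to what extent there are more AEs associated with treatment". Section 7.1 says: "Following DBPCFC2, assignment will be unblinded and placebo participants will be offered open-label active treatment"; section 7.5 repeats the offer.

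On who reaches DBPCFC3, section 5.6.1 says: "Participants receiving active treatment who react to <1443 mg peanut protein during DBPCFC2 will be considered a treatment failure". Section 7.7.2.2 also makes a participant a failure if 600 mg is not reached by week 50. Sections 9.1 and 9.2.2 take the per-protocol set to be active participants who complete DBPCFC3. Section 9.2.5 instead says that the Tolerance outcome is analysed in everyone who completes the modified rush visit.

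On the challenges, section 7.7.1 starts DBPCFC1 and DBPCFC2 at 3 mg and DBPCFC3 at 30 mg.

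**The concern.** The objective is causal: whether OIT induces increased tolerance. The criterion is any significant rise between two time points, with no minimum size and no reference to untreated participants. At least three things other than OIT can produce such a rise:

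- **Entry ceiling.** Participants must react at 443 mg or less at DBPCFC1, so some enter on an unusually low reading and regress upward later.
- **Omission of early failures.** If only DBPCFC3 completers are analysed, the active participants in whom OIT did not work are left out.
- **Different ladders.** A reaction at 3 or 10 mg can be recorded at DBPCFC1 but not at DBPCFC3.

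A placebo comparison on a common scale would remove the first and third. Counting every randomised participant would remove the second. As written, the objective can be declared met without evidence that OIT was responsible.

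**Working it through.** **1. The plan's own figures.** The documents give no power or sample size for this objective. The nearest figure is the Treg comparison in section 15.6: 8 versus 14, difference 1.5 SD, two-sided 5%, power 0.90. With the noncentral t, the noncentrality is 1.5 × √(8×14/22) = 3.38 on 20 df and power is 0.896, so it reproduces. It says nothing about the eliciting dose (ED).

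**2. How much of the interval has a control** (nominal days, section 7.4).
- DBPCFC1 to DBPCFC3: 518 − 28 = 490 days = 70 weeks.
- DBPCFC1 to DBPCFC2, placebo still blinded: 434 − 28 = 406 days = 58 weeks.
- DBPCFC2 to DBPCFC3, no secured control: 518 − 434 = 84 days = 12 weeks.

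**3. Who is measured** (sections 9.1, 15.5 and 15.6).
- 75% of 30 active participants desensitized = 22.5, used as 22. After 10% dropout the table has 7 + 12 = 19.
- Unmeasured at DBPCFC3: 30 − 22 = 8, or 30 − 19 = 11.
- Expected tolerance or partial tolerance: 8/30 = 27% of the arm, but 8/22 = 36% or 7/19 = 37% of those measured. These are responder proportions; they show what the choice of denominator does, not the bias in median ED.

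**4. The ladders** (section 7.7.1). Cumulative steps are 3, 13, 43, 143, 443 mg at DBPCFC1 and 30, 130, 430, 1430, 4430 mg at DBPCFC3. A participant who reacts at the first DBPCFC1 step cannot score below 30 mg at DBPCFC3: 30/3 = 10-fold with no change in sensitivity. From the second step the minimum is 30/13 = 2.3-fold.

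**5. Simulation with no OIT effect** (illustrative). Inputs: log-normal ED, median 45 mg and quartiles 4.5 and 200 mg from section 1.6.1, so log10 SD = log10(200/4.5)/1.349 = 1.22. Assumptions: within-person log10 SD of 0.2, 0.4 or 0.6; entry at 443 mg or less; observed ED taken as the next cumulative step; Wilcoxon signed-rank test, two-sided 5%, in 30 participants. Share of trials with a significant rise:

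| Within-person SD | Actual ladders, no drift | Common ladder, no drift | Common ladder, assumed 2-fold drift |
|---|---|---|---|
| 0.2 | 78% | 3% | 98% |
| 0.4 | 81% | 5% | 79% |
| 0.6 | 75% | 11% | 65% |

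The ladders are the main driver. The entry ceiling alone adds little. Drift matters only if it exists. A 30-versus-10 between-arm rank test, both arms on the same ladder, stayed at 4–6% throughout.

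**6. The between-arm alternative.** Comparing active DBPCFC3 with placebo DBPCFC2 brings the ladder problem back, because placebo DBPCFC2 starts at 3 mg. In null simulations without failure ranking (within-person SD 0.3–0.5, between-person SD 0.96–1.22), false positives were 7–12%, mostly favouring active. Treating the low doses as tied brought this to about 4–6%.

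**7. Precision.** For 30 versus 10, a 1.05 SD shift has noncentrality 1.05 × √(30×10/40) = 2.88 on 38 df, critical value 2.024, and power 80% (t-test approximation). A binary comparison is weaker: 8/30 versus 0/10 gives Fisher p = 0.165, and exact power is 26% even with a zero placebo rate.

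**The case against.** **The placebo arm does control most of the interval.** This stands. The between-arm criterion at DBPCFC2 addresses ED change to day 434. Section 1.2 does not promise control through DBPCFC3, so a reader might infer a contradiction that is not there. Nor do the documents support the stronger reading that a rise can never be attributed to OIT: 58 of the 70 weeks have randomised placebo data. What remains is that the tolerance objective does not use them.

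**The population is not fixed.** A reader might infer that the test is confined to active participants who passed DBPCFC2. That is a fair inference from sections 5.6.1, 9.1, 9.2.2 and 15.6, but no section says it for ED, and section 9.2.5 points elsewhere.

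**Upward natural drift is not shown.** This stands. The trial targets persistent allergy, and section 1.6.1 cites lower eliciting doses in patients over 10 than in the youngest tertile. The drift column above is an assumption.

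**Selection at DBPCFC2 may add little.** A reader might infer that chance passes inflate ED several-fold. With no treatment effect, only 0.5–4.6% of eligible participants would pass, against the 75% the plan expects. If a uniform treatment shift makes 75% pass, the residual rise beyond that shift is 1.08- to 1.52-fold among passers and 1.06- to 1.39-fold in everyone. Response that varies between people would add more, but the documents do not quantify it.

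**A large rise would be persuasive anyway.** Partly so. Partial Tolerance needs more than a 10-fold rise and at least 430 mg, which the low-dose ladder effect alone cannot reach. The ED objective has no such threshold.

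**It is one secondary objective in a phase I/II mechanistic study.** True. That limits the priority, but not the need to correct a causal claim.

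**Conclusion.** The point holds. Under the stated rule, a significant before/after rise would be read as OIT-induced tolerance although no comparator is used, the population is unsettled (8 to 11 of 30 active participants possibly unmeasured) and the two challenges record low doses differently. With no OIT effect the rule can succeed often: 75–81% of simulated trials on the actual ladders, 3–11% on a common ladder without drift. These rates rest on a log-normal ED taken from the section 1.6.1 quartiles, assumed within-person variability and an assumed test, since the plan names none. They show direction and mechanism and do not forecast this trial; a narrower baseline spread would lower the first figure. The ladder difference and the missing comparator can be read directly from the documents and need no simulation. The correction should be made because this is the protocol's stated clinical test of tolerance, but the primary Treg endpoint is not affected by this point.

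**What to change.** In sections 2.2.1, 3.1.2 and 9.2:

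1. Label the within-active DBPCFC1-to-DBPCFC3 change descriptive.
2. Base any inference that OIT increased tolerance on a rank-based comparison of all randomised participants: active DBPCFC1-to-DBPCFC3 change against placebo DBPCFC1-to-DBPCFC2 change.
3. Rank active participants who fail before DBPCFC3 as no increase, and write down the rule for other missing challenges in either arm.
4. Score all EDs on a common scale, with EDs below the first DBPCFC3 dose step treated as tied at the lowest category. This is a scoring rule only; the challenge schedules are unchanged.
5. Reconcile sections 5.6.1, 9.1, 9.2.2 and 15.6 with section 9.2.5, and state the population for this endpoint.

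The cost is wording and one added analysis, with no new visits or participants. State the downsides: the placebo reference is 12 weeks earlier than DBPCFC3; ranking failures as no increase is conservative for active, because placebo participants keep their measured changes; with 10 placebo participants the shift detectable with 80% power is about 1.05 SD; and the estimate will be less favourable than in completers. If the between-arm analysis is not wanted, the minimum is item 1, item 5 and removal of the causal wording.
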